7.4.3 Response to Hypoglycemia

- Patients are encouraged to check their BG for any symptoms of hypoglycemia.
- Patients will be permitted to take 15 grams of carbohydrates for any BG value <60 mg/dL. Trial staff will ensure proper functioning of the BP, infusion set, and insulin pump, and will encourage the patient to wait for the BP to treat the low blood sugar for as long as they feel comfortable.
- Patients will be required to take 15 grams of carbohydrates for any BG value <50 mg/dL. After treatment of hypoglycemia, a follow-up measurement will be taken 15 minutes later. Repeated measurements will be taken every 15 minutes until the BG is >60 mg/dL. Treatment will be repeated if subsequent BG values are still <50 mg/dL. All carbohydrate treatments for hypoglycemia will be documented by trial staff (amount and time).
- Trial staff will check the infusion site, BP, and insulin pump for normal operation any time hypoglycemia occurs. If there is any suspicion of infusion set malfunction, the site should be replaced. Trial staff will check the BP for any malfunction and correct any problems that are found.
- If no correctable fault is found, but there is doubt regarding the correct function of the BP system, an entirely new backup BP system may be started.
- If a patient experiences a seizure or unconsciousness associated with hypoglycemia, his or her participation in the trial will be discontinued.

Clinical Trial Protocol
ZP4207-16051

Version number: 8.0
Amendment 7.0
Date: 06 January 2017

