7.4.2 Data Collected During the Treatment Visits

- CGM glucose every 5 minutes from the Dexcom G4 Platinum CGM
- All BG measurements taken
- Insulin total dose by the BP and the patient's own insulin pump
- Glucagon total dose
- Timing and content of the meal eaten and carbohydrate amount
- Timing of meal announcement and size of meal announced
- Timing and glucose values at calibrations
- Timing and amount of carbohydrates taken for hypoglycemia
- Time patients were not under BP control for any reason
- List of technical faults associated with the BP including cause and resolution

Clinical Trial Protocol
ZP4207-16051

Version number: 8.0
Amendment 7.0
Date: 06 January 2017

- ZP4207/glucagon sampling will be collected at least hourly. If BG is <150 mg/dL, more frequent samples for plasma ZP4207/glucagon may be drawn at the discretion of the Investigator.
- Plasma glucose sampling will be collected at least hourly in parallel with ZP4207/glucagon exposure sampling. If BG is <150 mg/dL, then sampling will be every 30 minutes. If BG is <100 mg/dL, then sampling will be every 20 minutes. If BG is <80 mg/dL, then sampling will be every 10 minutes.
- Nausea and infusion site pain on a VAS at visit start (after insertion and before any drug administration), hourly, and at visit end
- Infusion site reaction according to the Draize scale at visit start (after insertion and before any drug administration), hourly, and at visit end
- Patient reports of symptoms, any other complaints, and AEs
- Vital signs including body temperature and blood pressure (at visit start and visit end) and weight
- Orthostatic vital signs (heart rate and blood pressure) in the seated position and within 3 minutes of standing
- Concomitant medications
- Chemistry and hematology samples (see [Appendix B](#)) at visit start and immediately after end of exercise
- ADA (Visit 3 only)
- 12-lead ECG at visit start and visit end
- Urine HCG pregnancy test for women of childbearing potential

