8.2.2 Glycemic

All of following metrics will be generated from the Dexcom G4 Platinum CGM data during each treatment visit:

- Fraction of time spent within each of the following glucose ranges:
 - <50 mg/dL
 - <60 mg/dL
 - <70 mg/dL
 - 70-120 mg/dL
 - 70-140 mg/dL
 - 70-180 mg/dL
 - >180 mg/dL
 - >250 mg/dL
 - >300 mg/dL
- Number of severe hypoglycemic events (patients unable to self-treat, requiring the assistance of another person)
- Number of episodes of symptomatic hypoglycemia
- Number of carbohydrate interventions for hypoglycemia
- Total grams of carbohydrates taken for hypoglycemia
- Mean CGM glucose

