10.5 Hypoglycemia

Hypoglycemia will be regarded as an AE and will be recorded and documented on an AE Form. For the purposes of AE reporting, the following definitions of hypoglycemia will be used:

- Symptomatic hypoglycemia: an event during which typical symptoms of hypoglycemia are accompanied by a BG concentration ≤ 70 mg/dL
- Asymptomatic hypoglycemia: an event not accompanied by typical symptoms of hypoglycemia but with a BG concentration ≤ 50 mg/dL
- Severe hypoglycemia: an event requiring assistance of another person to actively administer carbohydrates, glucagon, or take other corrective actions

Clinical Trial Protocol
ZP4207-16051

Version number: 8.0
Amendment 7.0
Date: 06 January 2017

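### Symptom status decides whether a glucose above 50 and up to 70 mg/dL is a hypoglycemia event, but the protocol ties no symptom question to a low value and names CGM as the source of the symptomatic-episode count

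*Protocol*

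**What the plan says.** Section 10.5 of the protocol (version 8.0, Amendment 7.0) makes hypoglycemia an adverse event and defines three kinds. Symptomatic: "an event during which typical symptoms of hypoglycemia are accompanied by a BG concentration ≤ 70 mg/dL". Asymptomatic: "an event not accompanied by typical symptoms of hypoglycemia but with a BG concentration ≤ 50 mg/dL". The third is worded "Severe hypoglycemia: an event requiring assistance of another person to actively administer carbohydrates, glucagon, or take other corrective actions" and has neither a glucose threshold nor a symptom criterion. The clarification memorandum to Amendment 7.0 adds that hypoglycemia adverse events are judged on plasma glucose values.

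The number and type of adverse events belong to the primary endpoint (Section 8.1). Section 8.2.2 lists as a secondary endpoint "Number of episodes of symptomatic hypoglycemia", under an opening line that attributes every metric in the list to the CGM. Section 11.2.2 summarizes the event counts descriptively and tests the proportions with Fisher's exact test where the data permit.

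For the treatment visits, Section 7.4.2 schedules glucose closely: "If BG is <80 mg/dL, then sampling will be every 10 minutes". Symptoms appear in the same list only as "Patient reports of symptoms, any other complaints, and AEs", with no time point. Section 7.4.3 says "Patients are encouraged to check their BG for any symptoms of hypoglycemia". The trial is open-label (Section 3.1).

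**The concern.** A symptomatic event needs two facts recorded together: a glucose value and the presence of symptoms at that value. The first is obtained by staff on a fixed schedule. The second has no fixed trigger. Whether a value of, say, 62 mg/dL becomes an adverse event can then depend on whether symptoms happened to be mentioned, noticed or asked about at that moment, by people who know which drug is being infused.

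Two arms with the same glucose profile and the same symptoms could show different symptomatic-episode counts and different adverse-event totals. An analysis plan cannot recover a symptom status that nobody recorded at the bedside.

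**Working it through.** **Step 1. Where symptom status decides the outcome.** Applying Section 10.5 to a non-severe low:

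| Glucose (mg/dL) | Symptoms recorded | No symptoms recorded |
|---|---|---|
| above 50, up to 70 | symptomatic event, AE | no event |
| 50 or below | symptomatic event, AE | asymptomatic event, AE |

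In the upper row symptom status changes both the adverse-event total and the Section 8.2.2 count. In the lower row it changes only the type of event and the Section 8.2.2 count. Every non-severe low at or below 70 mg/dL therefore needs a recorded yes or no.

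**Step 2. How each half is collected at Visits 3 and 4.**

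- Glucose: every 10 minutes below 80 mg/dL (Sections 7.4.1, 7.4.2, 9.2), and every 5 minutes below 80 mg/dL during exercise (Section 7.4.1).
- Nausea and infusion-site pain: asked on a VAS at visit start, hourly and at visit end (Section 7.4.2).
- Hypoglycemia symptoms: a review of reports at arrival (Section 7.4.1), untimed patient reports (Section 7.4.2), and the advice in Section 7.4.3 to check glucose when symptoms occur.
- General safeguards: patients must be asked about adverse events at each visit or telephone contact, and events the investigator observes are recorded too (Section 10.3). A nurse or physician is with patients throughout (Section 7.4.8).

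No section of version 8.0 makes a low value prompt a symptom question.

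**Step 3. The stated source.** A CGM trace holds glucose only. The symptomatic-episode count cannot be generated from it, and the Section 10.5 definition rests on plasma glucose plus symptoms.

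**Step 4. Scale, by illustration.** The plan has no figure to reproduce: Section 11.2.4 reports no formal sample size calculation, and no event rate is given. Assume, purely for scale, 10 patients per arm (Section 3.3 expects up to 10 completers per part), of whom a share p = 0.6 truly have k symptomatic lows each in both arms. Each low is recorded independently with probability q.

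- Recorded episodes = 10 × p × k × q
- Patients with at least one recorded episode = 10 × p × (1 − (1 − q)^k)

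| k | Episodes, q = 0.9 | q = 0.7 | q = 0.5 | Patients, q = 0.9 | q = 0.7 | q = 0.5 |
|---|---|---|---|---|---|---|
| 1 | 5.4 | 4.2 | 3.0 | 5.4 | 4.2 | 3.0 |
| 2 | 10.8 | 8.4 | 6.0 | 5.9 | 5.5 | 4.5 |
| 3 | 16.2 | 12.6 | 9.0 | 6.0 | 5.8 | 5.25 |

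For k = 3 and q = 0.5: episodes 10 × 0.6 × 3 × 0.5 = 9.0; patients 10 × 0.6 × (1 − 0.125) = 5.25. With no true difference, the episode ratio is 0.9/0.7 = 1.29 or 0.9/0.5 = 1.8, whatever p and k are. With equal q the arms agree. The patient counts converge as k rises.

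**Step 5. Effect on the planned test.** With 10 per arm, Fisher's exact test gives p = 0.0867 for 4/10 versus 0/10 and p = 0.0325 for 5/10 versus 0/10. The largest expected gap in the table is 5.4 − 3.0 = 2.4 patients, so uneven recording of this size would rarely drive the test. It would show in the event counts.

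**The case against.** The strongest reply is that symptoms are not simply left for the patient to bring up. Section 10.3 obliges staff to ask about adverse events at each contact and to record what they observe, hypoglycemic episodes are listed adverse events (Section 10.1), and staff are always present. A reader might infer from Sections 7.4.2 and 7.4.3 that symptoms are recorded only if volunteered. The documents do not support that. What remains is narrower: a general question per visit or telephone contact is not a symptom question at each low, and it does not match symptoms to a glucose value, as Section 10.5 requires.

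A reader might also infer that the comparison is biased toward one drug. That is not supported either. Both arms use the same device and algorithm within each part, each patient serves as their own control, so a stable habit of under-reporting acts on both arms, and nothing indicates which way reporting would differ. The reporting rates above are assumptions.

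Third, Section 12.1 leaves eCRF detail to the Data Management Plan, so the adverse-event form may already hold a symptom field. That is possible, but a field does not instruct anyone to ask at the time of the low.

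Finally, other measures do not depend on symptom reporting: CGM time below 50, 60 and 70 mg/dL, and the number and grams of carbohydrate interventions. The exposure measure named in Section 2.2 is CGM time below 60 mg/dL. This stands in full and limits what is at stake.

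**Conclusion.** The point holds as a gap in data capture and an error in a stated source. Section 10.5 makes symptom status decisive for every non-severe low at or below 70 mg/dL, version 8.0 ties no symptom question to such a value, and Section 8.2.2 attributes the symptomatic-episode count to a source that cannot supply it. In an open-label trial, the secondary endpoint and part of the adverse-event count are open to uneven ascertainment.

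The size and direction cannot be derived from the documents. Ratios of 1.29 to 1.8 in episode counts follow only from assumed recording rates of 90% against 70% or 50%. The consequence is mainly for descriptive counts. These still matter, because Section 11.2.4 justifies the sample size by the aim of exploring safety. The change is a cheap improvement worth making, not a threat to the trial's validity.

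**What to change.** In Sections 7.4.1 and 7.4.2, add that at every scheduled glucose at or below 70 mg/dL at Visits 3 and 4, in both arms, staff ask one fixed yes/no question on typical hypoglycemia symptoms and record the answer with that value. Use the answer for the Section 10.5 classification and the Section 8.2.2 endpoint, and keep spontaneous reports as an addition. Count consecutive readings at or below 70 mg/dL as one episode, symptomatic if any of its answers is yes; otherwise repeated draws would multiply one event. In Section 8.2.2, state that this endpoint comes from measured glucose plus recorded symptoms, not from CGM. Apply the change to both treatment visits of any patient, so that it does not split a within-patient comparison.

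The cost is one eCRF field, if none exists already, and a few seconds at draws already planned. More symptomatic events will be recorded in both arms. The answer still comes from an unblinded patient, so the open-label weakness is reduced, not removed. No treatment rule changes.

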7.4.4 Response to Hyperglycemia

- Trial staff will check the infusion site, BP, and insulin pump for normal operation any time BG is >300 mg/dL. If there is any suspicion of infusion set malfunction, the site should be replaced. Trial staff will check the BP for any malfunction and correct any problems that are found. If the BG remains >300 mg/dL for 2 hours despite troubleshooting, blood ketones will be measured. If the blood ketone result is >1.5 mmol/L, the visit will be stopped and rescheduled. The patient will be provided with insulin and a syringe to give an injection based on their correction factor.
- If a patient experiences diabetic ketoacidosis, his or her participation in the trial will be discontinued.
- If no correctable fault is found, but there is doubt regarding the correct function of the BP system, the treatment visit may be stopped and the visit rescheduled.

7.4.5 Response to Nausea/Vomiting

If significant nausea (e.g., that prevents the patient from eating normally) or any vomiting occurs, trial staff will notify the Investigator. Trial staff will assist the patient in troubleshooting, such as checking BG and the calibration of the CGM (excessive glucagon dosing may occur if the CGM is reading lower than the true BG). If a patient experiences persistent nausea and vomiting thought to be related to glucagon dosing, his or her participation in the trial will be discontinued.

7.4.6 Response to Other Medical Needs

If patients experience urgent or emergent medical concerns outside the scope of diabetes care and their primary care physicians, they will be taken to the MGH walk-in clinic or emergency room, or if necessary call 911.

7.4.7 Monitoring of Bionic Pancreas Performance

Bionic pancreas inventors and developers [REDACTED], [REDACTED], and/or an engineer trained by them will be readily available by phone for consultation for the trial staff at all times during the course of the trial.

7.4.8 Supervision by Trial Staff

A trial MD will be on call at all times during the course of the trial. An RN or MD will be with the trial patients in the Diabetes Research Center at all times.

7.5 Anti-drug Antibodies Assessment Visit (Visit 5)

Patients will return for an ADA Assessment Visit 10 days \pm 3 days following the last day of dosing (Visit 4) for ADA sampling and a review of AEs and concomitant medications.

7.6 Follow-up Visit (Visit 6)

Patients will return for a Follow-up Visit 25 days \pm 4 days following the last day of dosing (Visit 4), for chemistry, hematology, and ADA sampling, and a review of AEs and concomitant medications.

Clinical Trial Protocol
ZP4207-16051

Version number: 8.0
Amendment 7.0
Date: 06 January 2017

8 ENDPOINTS

8.1 Primary Endpoint

The primary endpoint is the safety and tolerability of ZP4207 in the BP using either the iLet or the iPhone platform as assessed by:

- Number and type of AEs
- Clinical laboratory measurements
- Vital signs
- 12-lead ECG
- Local tolerability and infusion site reactions as measured with the Draize scale
- Immunogenicity as measured by ADA
- Pain as measured on a 10 cm VAS
- Nausea as measured on a 10 cm VAS

8.2 Secondary Endpoints

The secondary endpoints include measurements of BP function as well as glycemic and non-glycemic measurements.

8.2.1 Bionic Pancreas Function

This endpoint data will be generated from the BP data during each treatment visit:

- Average percent insulin dose amounts calculated by the BP control algorithm that are successfully delivered by the pump
- Average percent glucagon/ZP4207 dose amounts calculated by the BP control algorithm that are successfully delivered by the pump
- Average percent dose amounts successfully issued to the pump by the BP control algorithm that are successfully delivered by the pump (calculated doses are not issued unless the pump is accessible and its delivery channel is available)
 - Average percent insulin dose amounts successfully issued to the pump by the BP control algorithm that are successfully delivered by the pump
 - Average percent glucagon/ZP4207 dose amounts successfully issued to the pump by the BP control algorithm that are successfully delivered by the pump
- Average percent dose amounts calculated by the BP algorithm that are successfully issued to the pump by the BP (calculated doses are not issued unless the pump is accessible and its delivery channel is available)
 - Average percent insulin dose amounts calculated by the BP control algorithm that are successfully issued by the BP
 - Average percent glucagon/ZP4207 dose amounts calculated by the BP control algorithm that are successfully issued by the BP
- Average percent of 5-minute steps during which the BP is functioning nominally in all respects based on real-time CGM data (new CGM glucose reading captured, dose calculated, and dose issued to pumps)
- Average percent of 5-minute steps during which the BP is functioning nominally with or without a new CGM glucose reading captured (dose calculated and dose issued to pumps). If a CGM signal is not available, the dose calculated may be based on weight or historical basal rates.
- CGM reliability index, calculated as percent of possible values actually recorded by CGM

Clinical Trial Protocol
ZP4207-16051

Version number: 8.0
Amendment 7.0
Date: 06 January 2017

- CGM Mean Absolute Relative Difference versus time-stamped BG values from meter download
- List of technical faults associated with the BP including cause and resolution

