6.7 Other Trial Devices

YSI 2300 STAT Plus™ (Yellow Springs Instruments): The YSI 2300 STAT Plus is an FDA-approved glucose analyzer. Blood glucose measurements using the YSI 2300 STAT Plus will be obtained off of the intravenous (IV) line during both treatment visits.

Nova Biomedical StatStrip Xpress Glucose Meter: The Nova StatStrip Xpress glucose meter is an FDA-approved glucose meter that is commercially available. Blood glucose measurements for CGM calibration will be obtained with the Nova StatStrip Xpress during both treatment visits if the YSI 2300 STAT Plus fails and via fingerstick with the Nova StatStrip Xpress during any periods when IV blood samples are not available for any reason or the IV fails.

Exercise Bike: The trial will utilize a stationary exercise bike (ergometer) for the in-clinic exercise at the treatment visits. This bike will be stored at the Diabetes Research Center when not in use.

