7.4 Treatment Visits (Visit 3 and Visit 4)

- Visit 3 will take place at least 48 hours after screening (Visit 1) and no more than 30 days after screening (Visit 1).
- There will be a 24-hour minimum washout between Visit 3 and Visit 4 and a maximum of 3 weeks between Visit 3 and Visit 4.
- Up to 2 patients may participate per day.
- In Part 1, each patient will participate in 2 treatment visits: 1 with the iPhone-based BP using ZP4207 and 1 with the iPhone-based BP using Lilly glucagon in a randomized order.
- In Part 2, each patient will participate in 2 treatment visits: 1 with the iLet using ZP4207 and 1 with the iLet using Lilly glucagon in a randomized order.
- The night before the treatment visit, patients will place a Dexcom G4 CGM sensor in the abdominal skin and calibrate the sensor when prompted using the provided Nova StatStrip Xpress meter. Patients will be instructed to call if they encounter any difficulty with their CGM.
- Patients will be responsible for their own medications other than insulin during the trial. Any medical advice needed by the patients during their participation that is not directly related to BG control should be obtained from them in their usual manner. Patients may take any over-the-counter medications that they wish during the trial, with the exception of any medication containing acetaminophen as that may cause interference with CGM sensing. If patients experience urgent or emergent medical concerns outside the scope of diabetes care and their primary care physicians, they will be taken to the MGH walk-in clinic or emergency room, or if necessary call 911.
- During the trial, patients will not use any recreational drugs or drugs of abuse. The need to take prescription drugs that dull the sensorium, reduce sensitivity to symptoms of hypoglycemia, or hinder appropriate decision-making may be grounds for exclusion from the trial or discontinuation of participation, a decision that will be made by the Investigator.
- Patients will be instructed concerning diabetes management (e.g., basal insulin rate adjustment by insulin pump) during fasting prior to and between the treatment visits per the medical judgment of the Investigator.
- Patients will not tamper with the BP, including changing any settings.
- Patients may not remove the BP during the trial unless the BP failed or they are withdrawing from the trial.
- The exact time of each procedure and assessment will be documented.

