 - The basal rate of the patient's own insulin infusion pump will be changed to be 2-fold higher than weighted mean of the basal rate during the trial period. This is intended to increase the usage of glucagon during the treatment visit. The basal insulin rate may be decreased during the treatment visit at the discretion of the Investigator. To the extent possible, the same basal rate should be used at Visit 3 and Visit 4.
 - The patients will continue to wear their own infusion pump infusing at the temporary basal rate throughout the visit until the start of the structured exercise period, in addition to the BP.
 - The staff will start the BP as close as possible to a minute divisible by 5 minutes (i.e., on a 5-minute mark). The starting time will be considered Hour 0.
 - Additional calibrations will be performed at any of the BG checks throughout the day if the CGM value does not meet the ISO standard (<15 mg/dL difference for BG values <75 mg/dL; <20% absolute difference for BG values >75 mg/dL) at the time of the BG measurement AND it is a good time to calibrate (the CGM trend arrow is flat and there has been no carbohydrate intake in the last 30 minutes or glucagon boluses in the last 15 minutes).
 - Blood samples will be taken from the IV at least hourly and processed for plasma ZP4207/glucagon. If BG is <150 mg/dL, more frequent samples for plasma ZP4207/glucagon may be drawn at the discretion of the Investigator. The actual time of sampling will be recorded in the eCRF.
 - Plasma glucose samples will be taken from the IV at least hourly in parallel with ZP4207/glucagon exposure sampling and measured using the YSI 2300 STAT Plus. If the YSI 2300 STAT Plus and/or IV fails, the Nova StatStrip Xpress will be used for glucose measurements. If BG is <150 mg/dL, then sampling will be every 30 minutes. If BG is <100 mg/dL, then sampling will be every 20 minutes. If BG is <80 mg/dL, then

Clinical Trial Protocol
ZP4207-16051

Version number: 8.0
Amendment 7.0
Date: 06 January 2017

sampling will be every 10 minutes. The actual time of sampling will be recorded in the eCRF.

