- Patients will exercise on a stationary bike with a heart rate from 120-140 beats per minute for a total of 4,000 heart beats (approximately 30 minutes). Patients will rate their exercise intensity using the Borg scale every 5 minutes, with the target intensity level between 12 and 14. Heart rate will be measured every 5 minutes.
- Chemistry and hematology samples will be collected immediately after end of exercise (see [Appendix B](#)).
- BG measurements will be obtained off of the IV line every 10 minutes. If BG is <80 mg/dL, BG measurements will be obtained off of the IV line every 5 minutes.
 - If BG is <50 mg/dL, the exercise will be terminated regardless of heart beats achieved.
 - Carbohydrates will be given for any BG <50 mg/dL according to the following protocol: Dextrose (g) = BSA (m²)/[1.7 m² (women) or 1.9 m² (men)] *15 g.
 - Repeat treatments will be given at 15-minute intervals as long as BG remains <50 mg/dL.

Clinical Trial Protocol
ZP4207-16051

Version number: 8.0
Amendment 7.0
Date: 06 January 2017

- If there is an interruption in the Dexcom CGM output, trial staff will assist the patient in recovering CGM data streaming. If this requires replacement of the CGM sensor, BGs will be checked every 10 minutes (every 5 minutes if BG is <80 mg/dL) using blood from the IV until the CGM is able to be calibrated again. These BGs will be entered into the BP, which will treat them as CGM values and dose insulin and/or glucagon appropriately.
- If there is a complete failure of the BP operation, patients will take over their own BG control using their personal insulin pump until the BP can be brought back online. If BP control cannot be promptly resumed (e.g., within 30 minutes), the patient may be asked to repeat that trial day once.
- Patients may choose to withdraw from the trial at any time. If they withdraw from the trial, they should alert a provider immediately.
- Just prior to the end of the study visit, vital signs including body temperature and blood pressure will be obtained and a 12-lead ECG will be performed. Orthostatic vital signs (heart rate and blood pressure) will be measured in the seated position and within 3 minutes of standing. If patients have hypotension or orthostatic hypotension, discharge will be delayed until their blood pressure is normal and stable.

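### The CGM accuracy endpoint (MARD) is referenced to the glucose-meter download, but the visit procedures make the YSI analyzer the planned in-visit method and the meter a fallback

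*Protocol*

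**What the plan says.** **The endpoint.** Protocol 8.2.1, repeated in the synopsis, lists "CGM Mean Absolute Relative Difference versus time-stamped BG values from meter download" among the device-function endpoints. The lead-in sets the window: "This endpoint data will be generated from the BP data during each treatment visit".

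**The in-visit method.** Under 7.4.1, glucose samples are drawn from the IV at least hourly, "in parallel with ZP4207/glucagon exposure sampling and measured using the YSI 2300 STAT Plus". They become more frequent as glucose falls. The meter's role follows: "If the YSI 2300 STAT Plus and/or IV fails, the Nova StatStrip Xpress will be used for glucose measurements". Section 9.2 repeats both rules. During exercise, 7.4.1 adds that "BG measurements will be obtained off of the IV line every 10 minutes".

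**Calibration.** Section 6.7 applies the same order to in-visit calibration: "Blood glucose measurements for CGM calibration will be obtained with the Nova StatStrip Xpress during both treatment visits if the YSI 2300 STAT Plus fails". It also allows Nova fingersticks in any period without IV blood. Under 7.4, patients place a sensor the night before each treatment visit and "calibrate the sensor when prompted using the provided Nova StatStrip Xpress meter".

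**The devices.** Section 6.7 describes the YSI as an analyzer and the Nova as a glucose meter, under separate entries. Section 7.4.1 plans a download of the bionic pancreas and the glucose meters at the end of the visit, and mentions none for the YSI.

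**The concern.** The accuracy endpoint takes its reference from a device that the procedures hold in reserve. The only routine use given to the Nova by name is the patient's calibration the night before, which falls outside the treatment visit. If the equipment works as planned, the download should therefore contain little from the visit itself. Values that do arise from equipment trouble would cluster in those periods, and any entered as calibrations would not be an independent test of the sensor.

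Evaluating device reliability is a stated secondary objective (2.2). The CGM feeds the controller (6.5, 6.6) and supplies the time-in-range and mean glucose endpoints (8.2.2), so readers will want a credible estimate of its error. The trial collects a suitable reference series, but the endpoint definition points elsewhere.

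**Working it through.** The plan states no figure for the number of reference pairs, so there is none to reproduce. The check counts scheduled reference values by device.

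**Inputs**
- Time on the bionic pancreas: about 8 hours (7.4.1, stopped after approximately Hour 8).
- YSI sampling: at least hourly; every 30, 20 or 10 minutes when glucose is below 150, 100 or 80 mg/dL (7.4.1, 9.2).
- Patients: up to 10 per part, each with one visit per treatment arm (3.1).
- Nova readings scheduled by name during the visit: none found in 6.7, 7.4, 7.4.1, 7.4.2 or 9.2.

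**YSI values per visit** = 480 min / interval + 1, counting Hour 0 and Hour 8.

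| Interval held throughout | Values per visit |
|---|---|
| 60 min | 480/60 + 1 = 9 |
| 30 min | 480/30 + 1 = 17 |
| 20 min | 480/20 + 1 = 25 |
| 10 min | 480/10 + 1 = 49 |

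Only the first row is guaranteed by the schedule. It gives 9 × 10 = 90 per arm and 9 × 20 visits = 180 per part. Exercise samples come on top; values used as calibrations would come off.

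**Meter values per visit.** The documents give no failure rate. Assume that a share f of the hourly samples falls back to the meter:

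| f (assumed) | Per visit, 9 × f | Per part, 180 × f |
|---|---|---|
| 0% | 0 | 0 |
| 5% | 0.45 | 9 |
| 10% | 0.9 | 18 |
| 20% | 1.8 | 36 |

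Even at 20%, the meter yields fewer than 2 values per visit from this source.

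**Does a loose reading of the word meter rescue the endpoint?** Suppose it were meant to include the YSI. The memorandum of 25 January 2017 says that the YSI reports whole-blood glucose and that staff multiply by 1.12 for the plasma equivalent. Against unconverted YSI output, a sensor that read plasma glucose perfectly would show a relative difference of (1.12 − 1.00)/1.00 = 12%. The endpoint would still have to say that converted values are the reference.

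**The case against.** **Some meter values may exist with everything working.** Section 6.7 permits fingersticks whenever IV blood is unavailable, whatever the cause, which is wider than equipment failure. Section 7.4.1 requires a glucose check on arrival and lists IV placement later, so a fingerstick then is plausible, though before Hour 0. Section 7.4.3 encourages checks for symptoms without naming a device. The memorandum says IV blood serves both devices, and 6.6 says the iLet can communicate with the Nova. This stands as far as it goes: a reader might infer that the download holds no in-visit values and that MARD cannot be computed, and the documents do not establish that. But none of these passages schedules paired meter readings, and the memorandum repeats the fallback rule.

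**The night-before calibrations would not flatter the result.** A reader might infer that MARD would be computed on the values the sensor was set to and so look too good. Section 8.2.1 limits the endpoint to the treatment visit, so those values would not enter. The supported consequence is sparse, atypical data. An optimistic bias is not shown.

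**The YSI data are not wasted.** They are the pharmacodynamic assessment (9.2) and govern sampling frequency, and the memorandum bases clinical decisions and hypoglycemia reporting on plasma-equivalent values. The gap is only that they are not named as the MARD reference.

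**Details belong in the statistical analysis plan.** This holds for the pairing window and any breakdown by glucose range, and neither is faulted here. The reference source is different: the Protocol itself states it, and it conflicts with the Protocol's own procedures.

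**Conclusion.** The MARD definition is wrong as written. It names a reference that the visit procedures treat as a fallback, and no section reconciles the two. Followed literally, the endpoint would rest on a small number of unrepresentative values that cannot be fixed from the documents; the fallback shares in the check are illustrative assumptions. The firm figure is the other side: at least 9 YSI values per 8-hour visit, about 90 per arm of 10 patients before calibration values are removed.

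Two larger claims should be resisted. One would take 10-minute sampling over the whole visit and count 49 × 10 = 490 YSI values per arm; that would need glucose below 80 mg/dL throughout in every patient. The other would treat the defect as undermining every glycemic result. Sensor error matters to those results, but this sentence changes no time-in-range value, treatment comparison or safety assessment. One secondary device-function endpoint in a feasibility trial is affected, and the data needed to answer it are already planned. It should be fixed, and it is not critical to the trial.

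**What to change.** In 8.2.1 and the synopsis, define the endpoint as CGM MARD during each treatment visit against time-matched YSI glucose, expressed as plasma equivalent with the memorandum's factor of 1.12. State that Nova values serve only as a flagged fallback, and that values entered as CGM calibrations are excluded or reported separately. The pairing window and any breakdown by glucose range can go in the statistical analysis plan; a breakdown is useful because sampling is denser at low glucose.

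The cost is one line in two places plus a derivation rule. No new samples or procedures are needed: 7.4.2 already collects every glucose measurement, and 7.4.1 already requires actual sampling times in the eCRF. The change should be made before database lock, including any interim lock after Part 1, so that the reference is not chosen after the data are seen.
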